3 STUDY DESIGN

3.1 Description of the Study Design ([Figure 1](#))

The trial is a randomized double-blind placebo-controlled study to examine the effect of single infusions of VRC01 and 10-1074 in HIV-infected individuals undergoing sequential antiretroviral treatment interruptions. Participants will be randomized 1:1 to treatment with VRC01 plus 10-1074 or normal saline placebo. Study staff and participants will be blinded to treatment assignments.

First ATI

The day following study enrollment, subjects will stop ART (Day 0). Subjects taking non-nucleoside reverse transcriptase inhibitors (NNRTIs) will switch to a protease or integrase inhibitor-based regimen at least 2 weeks prior to Day 0 to ensure that the washout period of antiretroviral agents is roughly equal. During this first ATI phase of the study, HIV ribonucleic acid (RNA) levels and CD4⁺ T cell counts will be monitored every 2 weeks until plasma viremia of ≥ 200 copies/mL is detected.

VRC01 plus 10-1074/ Placebo Treatment Phase

Within 14 days of the first reported plasma viremia value of ≥ 200 copies/mL, subjects will be randomized 1:1 to receive single sequential infusions of VRC01 and 10-1074 or 2 sequential infusions of saline placebo. All subjects will restart ART the day following their bNAb/placebo infusions.

Second ATI

After re-institution of ART, subjects will have plasma viremia measured every 4 weeks. Twelve weeks after achieving ART-induced viral suppression subjects will undergo a second analytical treatment interruption. Viral suppression is defined as a plasma viremia < 40 copies/mL.

Transient “blips” in plasma viral levels are allowed as long as blips are < 400 copies/mL and succeeding viral levels return to < 40 copies/mL on subsequent testing.

[figure not shown]
During this second ATI, plasma viremia and CD4⁺ T cell counts will be monitored every 2 weeks and subjects will restart ART if they meet one or more of the following criteria prior to reaching ATI week 16:

- A confirmed $> 30\%$ decline in baseline CD4⁺ T cell count or an absolute CD4⁺ T cell count < 350 cells/mm³ that is associated with a HIV RNA level > 40 copies/mL.

- A sustained (>4 weeks) HIV RNA level of >1,000 copies/mL
- Any HIV-related syndrome (e.g. acute retroviral syndrome, opportunistic infection)
- Pregnancy

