14 STATISTICAL CONSIDERATIONS

Efficacy Analysis

The primary outcome is the time from the start of the second treatment interruption until the subject meets criteria to restart ART. The probabilities of remaining below restart criteria for different amounts of time will be displayed using Kaplan-Meier plots and compared using the log-rank test. Secondary analyses will compare time to other milestones such as VL>400 and VL>1,000.

Safety Analysis

The proportion of subjects with grade 3 or higher AEs will be computed in each arm, along with 95% exact confidence intervals using the Clopper/Pearson method. The between-arm difference in the proportion of subjects with an AE of grade 3 or higher will be compared using Fisher's exact test and its associated confidence interval obtained by inverting two 1-sided tests at alpha=0.025.

Sample Size

Using control data from another similar trial, we modeled the time T (in days) to meet restart criteria as a Weibull distribution with survival function $P(T>t)=\exp[-(\lambda t)^p]$, where $\lambda=\exp(-3.861)=0.021$ and $p=1.957$. From these parameters, we estimated the median time to meet restart criteria as 39.486 days in the control arm. We can express the treatment effect in terms of either the hazard ratio θ or the factor β by which treatment increases the median time to meet restart criteria; β and θ are related by $\beta=\theta^{-1/p}$.

Assuming 25 subjects per arm are followed for 180 days, nearly everyone in both arms would be expected to meet restart criteria by 180 days. Power for a 40%, 50%, and 60% reduction in hazard is approximately 44%, 69%, and 90%, respectively ([Table 2](#)). These hazard reductions correspond to 30%, 42.5%, and 60% increases in the median time to meet restart criteria. Therefore, power is approximately 90% if the bNAb increases the median time to meet restart criteria by 60% relative to the placebo arm.

Table 2. Power under different treatment effects, expressed as either reduction in hazard or percent increase in median time to meet restart criteria.

Reduction in hazard	% Increase in median time to meet restart criteria	Power
40%	30%	44%
50%	42.5%	69%
60%	60%	90%

In terms of safety, a sample size of 25 subjects in the bNAb arm provides approximately 93% probability of detecting at least one AE that occurs in 10% or more of the population.

Table 3. Probability that at least 1 of 25 people in the bNAb arm will experience an AE that occurs in at least 10% of the population.

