	AE frequency 1%	AE frequency 5%	AE frequency 10%
Probability of at least 1	22%	72%	93%

Futility

If results are sufficiently unpromising at the approximate halfway point (after 13 per arm have been evaluated for the primary outcome), the trial will be stopped for futility. Specifically, we will compute the conditional probability of a statistically significant result at the end of the trial, given the current data in each arm. This will be computed assuming a true treatment effect of a 60% increase in the median time to meet restart criteria. A recommendation for stopping for futility will be made if conditional power under this large assumed effect drops below 30%. This corresponds to seeing either no between-arm difference or a worse outcome in the bNAb arm at the approximate halfway point. A copy of the futility analysis will be made available to the DSMB.

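### Table 2's powers of 44%, 69% and 90% come from an approximation that overstates the planned log-rank test; on the 2-weekly visit schedule it has about 40%, 64% and 86%

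*Combined protocol and SAP*

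**What the plan says.** Section 14, Efficacy Analysis, defines the primary outcome as time from the start of the second treatment interruption to meeting the ART restart criteria. The arms are to be "compared using the log-rank test".

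Section 14, Sample Size, models control-arm time as Weibull with λ = exp(-3.861) and p = 1.957. Its premise is "Assuming 25 subjects per arm are followed for 180 days", and it adds that "nearly everyone in both arms would be expected to meet restart criteria by 180 days". It then gives the powers: "Power for a 40%, 50%, and 60% reduction in hazard is approximately 44%, 69%, and 90%, respectively". The summary sentence is "Therefore, power is approximately 90% if the bNAb increases the median time to meet restart criteria by 60% relative to the placebo arm". It names no power formula and no alpha for the efficacy test. The only alpha in the section belongs to the safety comparison.

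Two features of the design are not mentioned beside these powers. Section 3.1 says that in the second interruption viremia and CD4 counts "will be monitored every 2 weeks and subjects will restart ART if they meet one or more of the following criteria". The Futility paragraph of Section 14 adds a look after 13 per arm have been evaluated: "A recommendation for stopping for futility will be made if conditional power under this large assumed effect drops below 30" (percent).

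**The concern.** An event-count formula usually takes the variance of the log-rank statistic as one quarter of the events. That holds when the two arms stay about equal in the risk sets, which is the case near a hazard ratio of 1. Here the hazard ratios are 0.4 to 0.6 and almost every participant has an event. The control arm therefore empties first, later risk sets are unbalanced, and the information falls below events/4. The formula also takes event times as observed exactly, whereas the restart criteria are checked every 2 weeks.

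Both effects push the true power below the printed figure. What is at stake is the concluding claim of about 90% power for a 60% increase in the median. A reader of a null result will use that figure to judge how firmly the effect has been ruled out.

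**Working it through.** **Inputs.** From Section 14: 25 per arm; control survival exp[-(λt)^p] with λ = exp(-3.861) and p = 1.957; 180 days of follow-up; hazard ratios θ of 0.6, 0.5 and 0.4; log-rank test; futility look at 13 per arm with a 30% conditional-power threshold under a 60% median increase. From Section 3.1: assessments every 14 days. Assumed, because the plan does not state them: two-sided alpha 0.05, proportional hazards, no dropout.

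**Step 1: expected events.** By day 180 the model gives 49.99, 49.97 and 49.89 events out of 50 at θ = 0.6, 0.5 and 0.4. Fifty is the right count for the formula.

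**Step 2: reproduce the plan.** The median factors θ^(-1/p) are 1.298, 1.425 and 1.597, matching the printed 30%, 42.5% and 60%. The Schoenfeld power is Φ(|ln θ|·√(50/4) − 1.96):

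- θ = 0.6: Φ(0.511 × 3.536 − 1.96) = Φ(−0.154) = 43.9%
- θ = 0.5: Φ(0.693 × 3.536 − 1.96) = Φ(0.491) = 68.8%
- θ = 0.4: Φ(0.916 × 3.536 − 1.96) = Φ(1.280) = 90.0%

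All three rows match Table 2. One-sided 0.05 gives 56.4%, 79.0% and 94.5%, which does not match. Nor does the Freedman formula, Φ(√50·(1−θ)/(1+θ) − 1.96), which gives 42.4%, 65.4% and 85.8%. Two standard formulas thus differ by up to about 4 points at these effects, so the approximation needs checking against the test itself.

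**Step 3: simulate the planned test.** Weibull times were drawn for 25 per arm, and the log-rank test used the hypergeometric variance for ties and a critical value of 1.96. For the visit schedule, times were rounded up to the next 14-day visit. For futility, the first 13 per arm were analysed at information fraction t = 26/50 = 0.52. Conditional power was Φ((Z√t + 3.24(1−t) − 1.96)/√(1−t)), where 3.24 = −ln(0.4)·√12.5. Conditional power below 30% corresponds to an interim Z below about 0.06. Ranges are over runs of 40,000 to 80,000 trials per row (Monte Carlo standard error at most 0.25 points).

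| Power (%) | θ = 0.6 | θ = 0.5 | θ = 0.4 |
|---|---|---|---|
| Printed in Table 2 | 44 | 69 | 90 |
| Schoenfeld, 50 events | 43.9 | 68.8 | 90.0 |
| Log-rank, continuous times | 41.6–42.0 | 65.1–65.8 | 87.0–87.4 |
| Log-rank, 14-day visits | 40.0–40.4 | 63.9–64.2 | 86.0–86.4 |
| The same with futility stop | 39.7–40.1 | 63.5–63.9 | 85.8–86.1 |

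**Step 4: split the loss.** Replacing the formula by the actual test costs about 2 to 3 points, the 2-weekly schedule about 1 to 2, and the futility stop about 0.3. Upper-tail type I error on the visit schedule was about 0.025, so the loss does not come from an overly strict test.

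**Step 5: vary the assumptions (all with futility).**

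| Variant | θ = 0.6 | θ = 0.5 | θ = 0.4 |
|---|---|---|---|
| Visits shifted by up to 5 days (Section 6 window) | 40.2 | 63.7 | 86.0 |
| Rounding to the nearest visit | 40.0 | 63.9 | 86.1 |
| Censoring at week 16 (day 112) | 39.7 | 63.6 | 85.3 |
| Stopping when interim Z ≤ 0 | 39.8 | 63.7 | 85.9 |

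**Step 6: futility stop rates.** On the visit schedule the rule stops about 12%, 5% and 2% of trials at θ = 0.6, 0.5 and 0.4, and about 52% when there is no effect.

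**The case against.** The strongest reply is that nothing in Table 2 is miscalculated. Each figure follows from a standard formula, the text says the powers are approximate, and the trial is a Phase 1 exploratory study whose sample size would not change. That stands as to the nature of the problem. It does not remove the gap, which is 4 to 5 points in the same direction in every row.

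A second reply is that every figure depends on a Weibull fitted to control data of unstated size, with exact proportional hazards and no dropout, so 86% is conditional too. That is true. But the comparison holds those inputs fixed and changes only the approximation and the observation schedule, so uncertainty about the inputs is no reason to print the larger number.

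A third reply is that the simulation is not the full written rule. Section 3.1 has a week 16 provision for restarting ART, other events can trigger a restart, and visit dates can move within their window. Censoring at week 16 and shifting visits were both tried, and the gap remained. The shifted-visit result also shows that the loss comes from coarse observation rather than from exact ties.

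A reader might infer that the futility rule is a main cause of the shortfall, or that leaving out its stopping probabilities is an error. Neither is supported. The rule costs about 0.3 points. Section 14 already says in words what result it corresponds to, and the DSMB receives the analysis. It is also described once as a stop and once as a recommendation, so treating it as binding is itself an assumption.

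**Conclusion.** The concern holds as an overstated power, not as an arithmetic error. Under the plan's own model, the planned log-rank test on the 2-weekly schedule has about 40%, 64% and 86% power where Table 2 prints 44%, 69% and 90%. The chance of missing the effect is about 60%, 36% and 14%, against the implied 56%, 31% and 10%.

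This rests on two-sided alpha 0.05, proportional hazards, no dropout and the stated Weibull. That Table 2 used the Schoenfeld formula is an inference from an exact match in all three rows, not something the plan says.

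A reader might go further and conclude that the sample size is wrong. The documents do not require that: Section 14 sets no minimum power, and the design remains reasonable for an exploratory trial once its power is correctly described. For scale only, about 28 per arm on the same schedule would deliver roughly the printed figures (44.4%, 69.1% and 90.0%, before the futility stop).

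**What to change.** Keep 25 per arm. In Section 14, Sample Size:

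- Restate the powers in Table 2 and in the text as about 40%, 64% and 86%, described as simulated log-rank power on the 2-weekly schedule.
- Change the summary sentence to approximately 86% power for a 60% increase in the median.
- State that the efficacy test is two-sided at 0.05, if that is what was intended, and name the power method and its assumptions of proportional hazards and no dropout.

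Optionally, add the futility stop probabilities from Step 6 for the DSMB's use.

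The cost is one table and a few sentences, with no added participants or procedures. The only downside is a slightly less favourable stated power.

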15 ETHICS/PROTECTION OF HUMAN SUBJECTS

15.1 Informed Consent Process

Informed consent is a process where information is presented to enable persons to voluntarily decide whether or not to participate as a research subject. It is an ongoing conversation between the human research subject and the researchers which begins before consent is given and continues until the end of the subject's involvement in the research. Discussions about the research will provide essential information about the study and include: purpose, duration, experimental procedures, alternatives, risks and benefits. Subjects will be given the opportunity to ask questions and have them answered.

The subjects will sign the informed consent document prior to undergoing any research procedures. The subjects may withdraw consent at any time throughout the course of the trial. A copy of the informed consent document will be given to the subjects for their records. The researcher will document the signing of the consent form in the subject's medical record. The rights and welfare of the subjects will be protected by emphasizing to them that the quality of their medical care will not be adversely affected if they decline to participate in this study.

15.1.1 Non-English-Speaking Subjects

If a non-English-speaking subject is eligible for enrollment, the subject will be consented using the process outlined in the HRPP Standard Operating Procedure Number 12: Requirements for Informed Consent. All instances of use of the CC Short Written Consent Form will be reported to the IRB at the time of annual review. If the CC Short Written Consent Form is used three times or more for the same language, this will be reported to the IRB immediately.

Illiterate English-Speaking Subjects

As the majority of the subject populations from which the study subjects are drawn are literate, written consent will typically be provided. However, this population does have a small rate of illiteracy, and oral consent will be obtained for illiterate subjects as consistent with HRPP Standard Operating Procedure Number 12: Requirements for Informed Consent without separate IRB approval for each specific use. At Continuing Reviews, the NIH IRB will be informed of the number of illiterate subjects who provided consent verbally.

15.2 Participant Confidentiality

All records will be kept confidential to the extent provided by federal, state and local law. The study monitors and other authorized representatives of the Sponsor may inspect all documents and records required to be maintained by the Investigator, including but not limited to, medical records. Records will be kept locked and all computer entry and networking programs will be done with coded numbers only. Clinical information will not be released without written permission of the subject, except as necessary for monitoring by IRB, NIAID, OHRP, or the sponsor's designee.

16 DATA HANDLING AND RECORD KEEPING

16.1 Data Capture and Management

Study data will be maintained in CRIMSON and collected directly from subjects during study visits and telephone calls or will be abstracted from subjects' medical records. Source documents include all recordings of observations or notations of clinical activities and all reports and records necessary to confirm the data abstracted for this study. Data entry into CRIMSON will be performed by authorized individuals. Corrections to CRIMSON shall be tracked electronically with time, date, individual making the correction, and what was changed.

The investigator is responsible for assuring that the data collected are complete, accurate, and recorded in a timely manner.

16.2 Record Retention

The investigator is responsible for retaining all essential documents listed in the International Conference for Harmonization Good Clinical Practice Guidelines. Study records will be maintained by the PI for a minimum of 3 years and in compliance with institutional, IRB, state, and federal medical records retention requirements, whichever is longest. All stored records will be kept confidential to the extent required by federal, state, and local law. The FDA requires study records to be retained for up to 2 years after marketing approval or disapproval (21 CFR 312.62), or until at least 2 years have elapsed since the formal discontinuation of clinical development of the investigational agent for a specific indication.

Should the investigator wish to assign the study records to another party and/or move them to another location, the investigator will provide written notification of such intent to NIAID/OCRPRO with the name of the person who will accept responsibility for the transferred records and/or their new location. Destruction or relocation of research records will not proceed without written permission from NIAID/OCRPRO.

Appendix A: Schedule of Events

Study Time Point	Screening and Baseline		First ATI Phase			Treatment Phase						Second ATI Phase				Follow-up Phase		
	Screen	Base line	Week 2	Week 4	Weeks 6-End ATI	Infusion Visit	ART Start	Week 4	Week 8	Week 12-End Tx Phase	Last Dose of ART	Week 2	Week 4	Week 6-Week 16	Repeat-End ATI	Week 4	Week 12	Week 24
ASSESSMENTS																		
Consent	X																	
Vital Signs	X	X						X	X							X	X	X
H & P	X	X						X	X									
HIV Counseling		X																
MEDICATIONS																		
Last Dose of cART			X															
VRC01 & 10-1074 Infusion																		
Restart cART																		
CLINICAL LABS																		
CBC/Diff	X	X							X	X								
aPTT/PT	X																	
Acute/Hepatic /Mineral	X	X							X	X								
Urinalysis	X																	
Pregnancy*	X	X																
HBsAg, Anti-HCV, HCV RNA,	X																	
HLA Typing**		X																
RESEARCH LABS																		
HIV-1 RNA	X	X	X	X					X	X								
Flow Cytometry***	X	X	X	X					X	X								
Serum storage		X								X	X							
Plasma storage	X	X	X	X					X	X								
PBMCs storage			X							X	X							
Estimated Volume per Visit	30	106	33	88					10		96	96						
Continue Schedule of Procedures																		
Continue Schedule of Procedures until Subject's VL is < 40 copies for 12 Weeks																		
Continue Schedule of Procedures																		
PRN: as needed depending on when subject meets criteria to restart cART																		

* for women of childbearing potential

** if not already on file

***includes CD4⁺ T cell count

PRN: as needed depending on when subject meets criteria to restart cART
